**\* HLA TYPING RESULTS MUST BE AVAILABLE AT STUDY ENTRY**

**^** First LMP-T CELL ADMINISTRATION (Day 1) must be within 14 days of study enrollment

**#** OFF PROTOCOL TREATMENT: Chemotherapy is strongly recommended as per institutional guidelines

**%** Delayed response to RTX and/or LMP-specific T cells have been described. However, chemotherapy is strongly recommended for patients with PD or SD as per institutional guidelines

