### 1.2 Secondary Aims

- 1.2.1 To determine the percentage of eligible patients for whom a suitable LMP-specific T-cell product derived from a Third Party LMP-specific T-cell bank is available.
- 1.2.2 To estimate the response rate (RR) to three doses of RTX as single agent in children and young adults with newly diagnosed or relapsed EBV-Positive CD20-Positive PTLD after solid organ transplantation (SOT).
- 1.2.3 To estimate the 2-year event-free survival (EFS) of children and young adults with newly diagnosed, refractory or relapsed EBV-Positive CD20-Positive PTLD after SOT treated with RTX and/or LMP-specific T cells.
- 1.2.4 To estimate overall survival (OS) of children and young adults with newly diagnosed, refractory or relapsed EBV-Positive CD20-Positive PTLD after SOT treated with RTX and/or LMP-specific T cells.
- 1.2.5 To estimate the RR to LMP-specific T cells of newly diagnosed (without complete response to Course RTX1), refractory, and relapsed children and young adults with EBV-Positive CD20-Positive PTLD.
- 1.2.6 To estimate progression-free survival (PFS) of children and young adults with newly diagnosed, refractory or relapsed EBV-Positive CD20-Positive PTLD after SOT treated with RTX and/or LMP-specific T cells.
- 1.2.7 To describe the toxicity of Third Party LMP-specific T cells in children and young adults with newly diagnosed, refractory or relapsed EBV-Positive CD20-Positive PTLD after SOT treated with RTX and/or LMP-specific T cells.
- 1.2.8 To validate that absence of EBV viremia correlates with RR, EFS and OS.

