**3.1.7 Post Course LMP-TC1 Evaluation and Treatment Assignment**

For patients on Arm LMP-TC, a response evaluation and Callback must be submitted by Day 42 of Course LMP-TC1. Patients with PR or SD after LMP-TC1 and available suitably matched LMP-specific T-cell product will proceed to Course LMP-TC2. Patients with CR or PD after LMP-TC1 will go off protocol therapy.

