**and/or**

##### MTOR Inhibitors

Sirolimus (dose range per institutional guidelines) to achieve minimum level of 4 ng/ml

or

Everolimus (dose range per institutional guidelines) to achieve minimum level of 3 ng/ml

*For patients on combination therapy, the minimum level needs to be maintained at least for the calcineurin inhibitors.*

**Close monitoring of immunosuppression as per institutional guidelines is required. Calcineurin inhibitor and/or MTOR inhibitor levels are required weekly. If levels are subtherapeutic, adjust dose(s) as per institutional guidelines and repeat levels approximately every 48-72 hours until the therapeutic range has been reached. [See Section 4.4.5](#)**

**Course LMP-TC1 (42 days):** Patients with a suitable LMP-specific T-cell product will receive the closest HLA matched product at a dose of  $2 \times 10^7$  cells/m^2/dose on Days 0 and 7 followed by a response evaluation completed during Days 36-41 and submitted via the Callback form by Day 42 (see [Section 3.1.7](#)). Patients with CR at the end of LMP-TC1 have completed protocol therapy. Patients with PD at the end of LMP-TC1 go off protocol therapy with a recommendation to receive further chemotherapy per institutional guidelines.

**Course LMP-TC2 (42 days):** Patients with PR or SD after LMP-TC1 and with a suitable product available will be assigned to Course LMP-TC2 to receive two additional doses of LMP-specific T cells.

1. If the patient had a PR and a sufficient number of vials of cells remain, the LMP-TC2 doses should come from the same product used in LMP-TC1.
2. If the patient had SD and/or insufficient cells remain in the original product, the LMP-TC2 doses may be selected from another product if an additional suitably matched product is available.

Except for the Induction course (RTX1) up to the start of Arm LMP-TC or Arm RTX, all patients with progressive disease during protocol therapy will be taken off protocol therapy to receive chemotherapy according to institutional guidelines.

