## 9.3 Methods of Analysis

For the primary endpoint, the point estimate of the proportion successfully matched and treated (among all 3 Cohorts combined) will be the uniformly minimum variance unbiased estimator, and an exact one-sided binomial 95% confidence interval (adjusted for the interim analysis by the method of Jung and Kim)[37](#) will be used to get a lower bound for the actual rate of successful treatments as defined in the primary objective.

For the secondary endpoints:

- The proportion of eligible patients who are successfully matched will be assessed using the uniformly minimum variance unbiased estimator for the proportion and an exact one-sided binomial 95% confidence interval (adjusted for the interim analysis by the method of Jung and Kim) to get a lower bound for the actual rate.
- PFS (defined as time to first occurrence of progression or death (events) or loss to follow-up or survival to analysis date (non-events)), EFS (defined as time to first occurrence of relapse, second/secondary malignant neoplasm (SMN), death (events) or loss to follow-up or survival to analysis date (non-events)), and OS (defined as time to death (event) or loss to follow-up or survival to analysis date (non-events)) will be assessed using Kaplan-Meier estimates, both for all patients combined and also separately in each Cohort. Aim 1.2.8 will be assessed using the Log-Rank test for EFS and OS and the exact conditional test of proportions (Fisher's Exact test) for RR, both for all patients combined and stratified by Cohort.
- Response rates will be assessed using exact two-sided binomial 95% confidence intervals to get estimates of the response rate. Aim 1.2.2 will be evaluated in Cohorts A and B only (combined and separately), with response classified by comparing disease evaluation at the Week 3 evaluation to the baseline of disease evaluation at study entry using the criteria in Section 10.2. Patients with CR will be considered responders. For Aim 1.2.5, response will be classified by comparing disease evaluation at the Week 6 of LMP-CT1 evaluation to the baseline of disease evaluation at the Week 3 evaluation using the criteria in Section 10.2, both in all Cohorts combined and in each Cohort separately. Patients with CR or PR will be considered responders.
- Toxicities will be described using descriptive statistics. Toxicity monitoring and analysis will be performed based on "as treated".

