#### 9.4 Evaluability for Response

Eligible patients assigned to Arm LMP-TC will be considered evaluable for the primary endpoint (percentage successfully matched and treated). All 3 Cohorts will be combined into a single set of patients for the analysis.

All eligible patients will be evaluable for Aims 1.2.1, 1.2.8, and 1.3.2. For Aim 1.2.1, all patients who submit HLA typing by the end of the trial will be evaluable, regardless of the timing of the submission.

Any eligible patient who receives at least one dose of RTX will be considered evaluable for Aims 1.2.2–1.2.4 and 1.2.6.

Any eligible patient who receives at least one dose of LMP-specific T cells will be considered evaluable for Aims 1.2.5, 1.2.7, 1.3.1, and 1.3.3.

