#### 10.2.3 Arm LMP-TC

In addition to a baseline scan and/or endoscopy with biopsies, additional scans and/or endoscopy with biopsies to document response need to be obtained at the end of Course LMP-TC1 during Week 6 of that course. For patients assigned to Course LMP-TC2, there will be an additional evaluation time point with scans scheduled at week 6 of LMP-TC2.

For patients found to have progressive disease (PD) at either one of those evaluations, it is recommended to repeat scans in a 2-4 week time frame as per the Lugano classification to confirm progressive disease prior to changing therapy because inflammatory responses to LMP-specific T cells have been reported with a corresponding initial increase in size and metabolic uptake of involved lymph nodes.

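### The response rate to LMP-specific T cells (Aim 1.2.5) is read only after the first course, so the plan has no response rate for the two-course regimen that the protocol gives

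*Combined protocol and SAP*

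**What the plan says.** - **The aim.** Section 1.2.5: "To estimate the RR to LMP-specific T cells of newly diagnosed" patients without CR to induction, and likewise of refractory and relapsed patients. Nothing limits it to one course.
- **The analysis.** Section 9.3: "For Aim 1.2.5, response will be classified by comparing disease evaluation at the Week 6 of LMP-CT1 evaluation" with a pre-T-cell reference evaluation, and "Patients with CR or PR will be considered responders". The interval is exact, two-sided, 95%.
- **The denominator.** Section 9.4: "Any eligible patient who receives at least one dose of LMP-specific T cells will be considered evaluable for Aims 1.2.5", among other aims.
- **The second course.** Section 3.1.7: "Patients with PR or SD after LMP-TC1 and available suitably matched LMP-specific T-cell product will proceed to Course LMP-TC2". Sections 4.1.2.2 and 4.4.4 agree.
- **The second scan.** Imaging on Days 36-41 is item j of the required observations for LMP-TC2 (Section 4.5.2). It is repeated in Section 4.5.4, and Section 10.2.3 states that "there will be an additional evaluation time point with scans scheduled at week 6 of LMP-TC2".
- **Late response.** The Cohort C schema notes: "Delayed response to RTX and/or LMP-specific T cells have been described".

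**The concern.** The investigational treatment is up to two courses, and the second goes to PR and SD patients with a product. Response after that second course is assessed but enters no planned response rate. A patient with SD at Week 6 of LMP-TC1 stays in the denominator and counts as a failure whatever the LMP-TC2 scan shows.

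Three things depend on this. First, someone planning the randomized studies foreseen in Section 2.2 will want the response rate to the regimen as given, and the plan does not produce it. Second, response and harm are counted on different exposure: Section 9.3 monitors cytokine release syndrome and GvHD by patient-course, so LMP-TC2 toxicity counts while LMP-TC2 response does not. Third, Aim 1.2.8 relates EBV viremia to response without its own definition of response. If it borrows the Aim 1.2.5 classification, late responders are classed as non-responders there too.

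**Working it through.** **Is the second scan used elsewhere?** Section 9 has no best-response rule, no response rate after LMP-TC2 and no sensitivity analysis. Section 10.2.8 defines duration of response, but Section 9 plans no analysis of it. The LMP-TC2 scan can still supply a progression event for PFS. It is therefore unused for response rate, not unused altogether.

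**Which patients change category?** Compare the CR+PR rate at Week 6 of LMP-TC1 with best response over both courses.

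| After LMP-TC1 | LMP-TC2 given? | Effect on CR+PR rate |
|---|---|---|
| CR | No, protocol therapy complete | None |
| PR | Yes, if product | None, already a responder |
| SD | Yes, if product | Rises if CR or PR follows |
| PD | No, off protocol therapy | None |

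Only SD patients who later reach CR or PR matter. PR to CR would change only a CR-alone line.

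**Size.** The documents state no target, precision or sample size for Aim 1.2.5, so there is no figure to reproduce. The neighbouring primary-design figures do reproduce with the exact two-stage binomial: 75.3% power and 4.2% error at 23/30, and futility probabilities of 59.7% and 6.1%. None of them depends on how Aim 1.2.5 is defined.

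Let n be the patients with at least one T-cell dose, x the responders after LMP-TC1, and k the SD patients who convert after LMP-TC2.

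- Planned rate: x/n
- Rate after up to two courses: (x+k)/n
- Difference: k/n
- Exact 95% interval for r responders: lower limit is the 0.025 quantile of Beta(r, n-r+1); upper limit is the 0.975 quantile of Beta(r+1, n-r).

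I take n=30 (the primary-endpoint target in Section 9.2, if all are dosed) and n=23 (the number of successes needed there). Both x and k are assumptions.

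| n | x | k | Rate | Exact 95% CI |
|---|---|---|---|---|
| 30 | 15 | 0 (planned) | 50.0% | 31.3-68.7 |
| 30 | 15 | 1 | 53.3% | 34.3-71.7 |
| 30 | 15 | 3 | 60.0% | 40.6-77.3 |
| 30 | 15 | 6 | 70.0% | 50.6-85.3 |
| 23 | 12 | 0 (planned) | 52.2% | 30.6-73.2 |
| 23 | 12 | 3 | 65.2% | 42.7-83.6 |

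Each converter adds 1/30 = 3.3 points or 1/23 = 4.3 points, whatever x is.

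**Time between readings.** LMP-TC1 ends on Day 42 and LMP-TC2 may start up to 21 days later (Section 4.4.5). Its scan can therefore fall as late as 42 + 21 + 41 = 104 days after the first infusion, against Days 36-41 for the first scan.

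**The case against.** The best defence is that a single fixed reading is a legitimate, prespecified choice. It is uniform across patients, and Aim 1.2.2 is handled in the same way, at Week 3 of induction. A reader might infer that the planned rate is biased low. The documents do not support that: it is a proper estimate of response after the first course, and what is missing is a label and a companion figure. The plan gives no reason for stopping at the first course, and the aim is not worded as first-course.

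The two-course rate also has real weaknesses:

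- SD patients may receive a different product in LMP-TC2 (Section 4.5.3.1).
- Only patients with an available product get a second reading, so the rate depends partly on the bank's stock, and the number of assessments differs by patient.
- The schema's remark on delayed response names rituximab as well as T cells, so a late response need not be a second-course effect.

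These objections stand. They are reasons to add the rate as a descriptive figure and not to replace the planned one.

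The background does not settle the choice. The third-party phase 2 study in Section 2.5.4 gave four doses, which a patient here reaches only after LMP-TC2, but it reported response at 5 weeks as well as at six months. The autologous LMP-TC study in Section 2.5.5 gave two weekly doses, with more allowed later for PR or SD, much like this protocol.

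**Conclusion.** The gap is real and limited. Section 9.3 yields a valid first-course response rate under an aim that is not so limited, and no response rate for the regimen of up to two courses. Counting LMP-TC2 responses can only raise the CR+PR rate or leave it unchanged, by k/n. The value of k is unknown from the documents, and with samples this small the intervals for the two rates overlap widely.

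Three stronger readings should be avoided.

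- **That PR-to-CR conversions add to the understatement.** They cannot, because PR already counts as response.
- **That this is the only activity estimate for the trial.** Section 9.3 also plans PFS, EFS and OS, although these cover rituximab and T cells together. Aim 1.2.5 is the only planned response estimate for the T cells.
- **That using the second scan would show whether a second course adds anything.** There is no comparison group for LMP-TC2, so it would not.

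This is a secondary estimation aim. The primary endpoint, sample size, power and stopping rules do not use it. The change is worth making because it is cheap and uses scans already required.

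**What to change.** In Section 9.3:

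1. Keep the Week 6 LMP-TC1 rate, correct the course name, and label it *response after the first course*.
2. Add a prespecified best response (CR or PR, with CR also shown alone) through the last protocol T-cell evaluation: Week 6 of LMP-TC1, or Week 6 of LMP-TC2 for those who receive it. Use the same reference evaluation, the same denominator of all eligible patients with at least one T-cell dose, and an exact 95% interval. Label it *after up to two courses*.
3. Give a shift table from LMP-TC1 to LMP-TC2 response that shows whether the product changed. It will also show any PR patient who progresses in LMP-TC2 but remains a responder by best response.
4. State which response classification Aim 1.2.8 uses.

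The cost is some wording and one extra table, with no new scans, patients or treatment. The text should say that the added rate is descriptive, for the reasons given under the objection. One point needs confirmation: Section 3.1.7 requires a Callback with the LMP-TC1 response, but the documents describe none after LMP-TC2. The sponsor should check that the case report form captures the LMP-TC2 response.

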### 2.4.2 Rituximab (RTX) in PTLD

Therapy with single agent RTX is the standard of care in PTLD after hematopoietic stem cell transplantation (HSCT) and has rapidly become the most commonly used form of therapy in PTLD after SOT in pediatric patients. RTX as single therapy is widely used in adult solid organ recipients with PTLD with reported CR rate of 60.5%. Preliminary data of a phase 2 study in 40 pediatric SOT recipients with refractory PTLD showed a 69% CR and 16% PR rate for an overall response rate of 85%. Histologies consisted of 17 polymorphic PTLD, 7 monomorphic PTLD, 1 Hodgkin-like, and 1 unspecified histology. A French review reported twenty-six SOT recipients with PTLD between the ages of 3-67 years treated with single agent RTX. There were 10 cases of polymorphic PTLD and 15 cases of monomorphic disease. The overall response rate was 65% (15 CR and 2 PR). Of 15 CRs, 11 patients remained in CR with a median follow-up of 8 months. The United Kingdom Children's Cancer Study Group (UKCCSG) published a retrospective review of rituximab in childhood immunosuppression related lymphoproliferative disease that included 10 SOT recipients and 8 HSCT recipients with PTLD out of 22 patients. The other patients had either primary immunodeficiencies (n=2) or other prolonged acquired immunodeficiency states (n=2). Of the 19 patients with PTLD, 15 patients were treated with single agent rituximab and 5 achieved a CR and 2 a PR for a total response rate of 46.7%. The German Pediatric PTLD phase 2 protocol ("Ped-PTLD2005-Pilot") tested response stratified therapy with patients receiving three weekly doses of RTX at  $375 \text{ mg/m}^2$ . Patients with CR or PR after three doses of RTX continue with RTX monotherapy while non-responders (NR) are assigned chemotherapy. The one-year EFS using RTX monotherapy for this entire study overall was 53% confirming that much improvement is required for the treatment of this disease beyond using RTX as a single agent therapy. The group of responders (64% of total study population) that was treated with RTX alone had an overall EFS of 81% (Table 1). Long term follow-up data is available on 40 patients. Among the 14 patients who had achieved a CR after three doses of RTX there was only one relapse, confirming that this group of patients has an excellent prognosis. However, in the group of 17 patients who achieved a PR after three doses of rituximab only 11 patients (22.5% of the total study population)

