3.2.5 Prior Therapy

Patients must have fully recovered from the acute toxic effects of all prior chemotherapy, immunotherapy, or radiotherapy prior to entering this study.

- a. Myelosuppressive chemotherapy: Must not have received within 2 weeks of entry onto this study.
- b. Biologic (anti-neoplastic agent):
  - Cohort A and B: Patient must not have received therapy with anti-CD20 monoclonal antibodies within 90 days of entry onto this study.
  - Cohort C: Patient must have received Rituximab at 375 mg/m^2 weekly for at least 3 doses within the last 90 days prior to study enrollment.
- c. Radiation therapy (RT): Must not have received any prior radiation to any sites of measurable disease.
- d. Stem Cell Transplant (SCT): Must not have received any prior stem cell transplant.
- e. Investigational Therapy: Must not have received investigational therapy within 30 days of entry onto this study.
- f. Cellular Therapy: Must not have received prior EBV or LMP-specific T cells within 90 days of entry onto this study.
- g. T-cell Antibodies: Must not have received alemtuzumab or other anti-T-cell antibody therapy within 28 days of entry onto this study.

Please see [Section 4.1.3](#) for the concomitant therapy restrictions for patients during treatment.

3.2.6 Cohort C Only: HLA typing is available and will be submitted at the time of enrollment.

\

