**6.2.1 Source and Pharmacology**

Rituximab is a genetically engineered chimeric murine/human monoclonal antibody which binds specifically to the antigen CD20 (human B lymphocyte restricted differentiation antigen, Bp35) located on the surface of pre B and mature B lymphocytes of both normal and malignant cells. The antibody is an IgG1 kappa immunoglobulin containing murine light- and heavy-chain variable region sequences and human constant region sequences. Rituximab is composed of two heavy chains of 451 amino acids and two light chains of 213 amino acids and has an approximate molecular weight of 145 kD. It is produced in mammalian cell (Chinese Hamster Ovary) culture.

CD20 regulates an early step(s) in the activation process for cell cycle initiation and differentiation, and possibly functions as a calcium ion channel. Rituximab binds to the CD20 antigen on B lymphocytes and recruits immune effector functions to mediate B-cell lysis. Possible mechanisms of cell lysis include complement-dependent cytotoxicity and antibody-dependent cell mediated cytotoxicity. The antibody has been shown to induce apoptosis in the DHL-4 human B-cell lymphoma line.

In 83% of patients, circulating B cells were depleted within the first three doses of rituximab with sustained depletion for up to 6 to 9 months post-treatment. Serum levels and half-life are proportional to the dose and have ranged from 31.5 to 152.6 hours after the first infusion and 83.9 to 407 hours after the fourth weekly infusion of 375 mg/m^2. The wide range of half-lives may reflect the variable tumor burden among patients and the changes in CD20-positive (normal and malignant) B-cell populations upon repeated administrations.

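### Aim 1.2.5 cannot separate late rituximab effect from T-cell response, and its Week 3 baseline does not work for Cohort B patients already in CR or for Cohort C

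*Combined protocol and SAP*

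**What the plan says.** Section 1.2 gives Aim 1.2.5 as the response rate to LMP-specific T cells in newly diagnosed patients without CR after RTX1 and in refractory and relapsed patients. On scoring, Section 9.3 states that "response will be classified by comparing disease evaluation at the Week 6 of LMP-CT1 evaluation to the baseline of disease evaluation at the Week 3" assessment. It adds "Patients with CR or PR will be considered responders", and asks for results "both in all Cohorts combined and in each Cohort separately". On precision: "Response rates will be assessed using exact two-sided binomial 95% confidence intervals to get estimates of the response rate". There is no test or threshold. Section 9.4 makes any eligible patient with one T-cell dose evaluable, whatever the Week 3 result.

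The schedule for Cohorts A and B is:
- rituximab on Days 1, 8 and 15 (4.2.3);
- response evaluation on Days 18–21 (4.1.1);
- Callback by Day 22, or once the patient is medically stable, with LMP-TC1 starting within two weeks of it (3.1.6);
- T-cell response scan on Days 36–41 of LMP-TC1 (4.4.2). The delivery map in 4.4.1 lists items a–i, k and l at Day 0; CT is item j and first appears at Day 36.

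Cohort A enters Arm LMP-TC with PR, SD or PD (4.2.5). Cohort B enters whatever its response (4.1.2.2). Cohort C skips RTX1; it must have had rituximab "weekly for at least 3 doses within the last 90 days prior to study enrollment" (3.2.5), with no minimum gap since the last dose. The Cohort C schema notes: "Delayed response to RTX and/or LMP-specific T cells have been described". The schema for Cohorts A and B carries a similar note.

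**The concern.** The aim names one agent, but the interval over which response is scored opens within a week of the last dose of another active agent. The protocol acknowledges that rituximab responses can be delayed, and Section 9.3 makes no provision for it. Within Cohort A, patients still responding to rituximab at Week 3 (PR) are pooled with those who are not (SD, PD), so reporting by cohort does not help.

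The stated baseline also fails for two groups. A relapsed patient already in CR at Week 3 has nothing left to respond, yet is evaluable and would meet the responder definition by remaining in CR. A refractory patient has no Week 3 evaluation at all.

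Aim 1.2.5 is the only clinical efficacy measure tied to T cells: PFS, EFS and OS are defined for rituximab and/or T cells. Section 2.2 cites a third-party T-cell series with 64% response at 5 weeks and looks ahead to a randomised study, so readers will want to set this rate beside such figures.

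**Working it through.** **The plan's own figures.** No sample size or power is given for Aim 1.2.5. The primary design reproduces: summing P(X1 = x)·P(X2 ≥ 23 − x) over x = 10 to 15, with 15 patients per stage, gives 0.7531 at a true rate of 80% and 0.0424 at 60%, against 75.3% and 4.2% in Section 9.2. Nothing below alters this.

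**Timing in Cohorts A and B** (last rituximab Day 15; Callback Day 22; LMP-TC1 Day 0 on study Day 22 to 36)
- Baseline scan after rituximab: 18 − 15 = 3 to 21 − 15 = 6 days.
- First T-cell dose after rituximab: 22 − 15 = 7 to 36 − 15 = 21 days.
- Baseline scan to first T-cell dose: 22 − 21 = 1 to 36 − 18 = 18 days, all without T cells.
- Scoring after rituximab: 22 + 36 − 15 = 43 to 36 + 41 − 15 = 62 days, about 6 to 9 weeks.

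A late Callback or the 72-hour allowance shifts these figures.

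**Drug remaining.** Section 6.2.1 gives a half-life of "83.9 to 407 hours after the fourth weekly infusion", that is 83.9/24 = 3.5 to 407/24 = 17.0 days. Assuming simple exponential decay, 25–75% remains at day 7 and 2–42% at day 21. RTX1 has three doses, not four, so this is only a guide.

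**Improvement without T cells in the cited data**
- German pediatric study (2.4.2): "in the group of 17 patients who achieved a PR after three doses of rituximab only 11 patients" reached a lasting CR without chemotherapy. 11/17 = 64.7%, exact 95% CI 38.3–85.8%. The 22.5% of the study population reproduces as 11/49 = 22.4%. These patients continued rituximab, and the time of conversion is not given.
- Earlier rituximab-chemotherapy study (2.4.1): 8 of 12 with residual disease at the end of therapy reached CR with no further treatment. 8/12 = 66.7%, CI 34.9–90.1%, but after chemotherapy as well.

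**Illustration for inert T cells.** Pooled rate = (PR share of non-CR patients) × (late rituximab response among those in PR), with no late response assumed in SD/PD. The German PR share is 17/(49 − 14) = 17/35 = 48.6%, assumed to apply here.

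| Late response among Week 3 PR (assumed) | Pooled rate |
|---|---|
| 10% | 4.9% |
| 25% | 12.1% |
| 50% | 24.3% |
| 65% (11/17) | 31.4% |

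Varying the PR share from 20% to 60% widens the range to 2–39%.

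**Precision after a split.** With about 30 treated patients and a PR share near one half, each stratum has about 15. At about 50% response the exact 95% CI goes from 31.3–68.7% (15/30) to 26.6–78.7% (8/15).

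**The case against.** Much can be said for the plan. Resetting the baseline at Week 3 removes shrinkage already achieved on rituximab: a Week 3 partial responder must reach CR or shrink by a further half. This stands, and only rituximab effect arising after Days 18–21 can leak in. Some confounding is inherent in giving two agents in sequence, and this is a secondary estimation aim in a single-arm feasibility pilot. That also stands, and it limits the stakes.

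The size is poorly supported. The German 11/17 describes lasting CR on continued rituximab, not response at Week 6 after stopping it, and the lower assumed rates have no source. The German counts do not fully reconcile either: 14 CR, 17 PR and 17 SD/PD make 48 of 49, and Table 1 has 32 responders where the text implies 31. The 31% figure is therefore at most an illustrative upper bound under that PR share, not an estimate.

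On Cohort B, Section 10.2.4.2 limits objective response to patients with measurable disease at baseline. If baseline there meant the Week 3 scan, CR patients would drop out. Section 9.4 sets no such limit, and neither section says which prevails, so the ambiguity remains.

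A reader might infer that response is scored one to three weeks after rituximab. It is not: that is the gap to the first T-cell dose, in Cohorts A and B only. A reader might also infer that the rate is useless for planning the randomised study. That does not follow, since the study would compare rituximab plus T cells with rituximab alone, and a rate for the sequence is relevant to it.

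**Conclusion.** The point holds in a limited form. As defined, Aim 1.2.5 measures response after rituximab followed by T cells. Late rituximab effect may be included, and reporting only combined and by cohort gives no means of seeing how much. The documents do not support the stronger reading that delayed rituximab response is in fact being credited to T cells by a known amount. The 5–31% range for inert T cells rests on the German PR share, on assumed conversion rates, and on no late response in SD/PD patients.

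Two further gaps need no such assumptions. The responder rule in Sections 9.3 and 9.4 does not exclude Cohort B patients already in CR at Week 3, and the stated baseline does not exist for Cohort C. The primary endpoint, its power and the sample size are untouched. This is an inexpensive improvement to a secondary aim.

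**What to change.** Amend Section 9.3 for Aim 1.2.5:

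1. In Cohorts A and B, report response by Week 3 status: CR, PR, and SD/PD. Do not count patients already in CR at that baseline as T-cell responders; list separately whether they remain in CR. Present SD/PD as the less confounded estimate of T-cell activity, saying that it is not free of late rituximab effect.
2. In Cohort C, name the study-entry evaluation before LMP-TC1 as the baseline, and tabulate response by days since last rituximab.
3. Label the pooled figure *response after RTX followed by LMP-specific T cells*.
4. State how the evaluability rules in 9.4 and 10.2.4.2 fit together for this aim.

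The cost is SAP wording and one table. Week 3 response is already needed for the Callback, and rituximab within 90 days is already an eligibility item, though the sponsor should confirm that the last-dose date is captured. The statistical price is the wider stratum intervals shown above, so the split should be read descriptively. No visit, scan or treatment changes.
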